**【 2020/12/14 】**

## Design

This was a 4-week randomized, parallel, single-blind and sham-controlled trial, followed by another 4-week open-label intervention, to investigate the feasibility and efficacy of iTBS over the bilateral pSTS in children and adolescents with ASD at Chang Gung Memorial Hospital (CGMH, Linkou, Taiwan). There were 2 phases in this RCT, with one-month follow-up. Specifically, after baseline assessments, participants were randomized to the Active or Sham group (Phase 1, Baseline-Week 4). Given limited human resources, the investigator ([name]) and his assistant assessed and delivered rTMS to all participants. Therefore, only participants and their caregivers were blind to the treatment condition (single-blind). Active versus sham iTBS was administered over the pSTS 2 days/week for 4 weeks. Entering Phase 2 (Week 5-8), participants were unblinded, and then active iTBS over the pSTS were administered to all participants 2 days/week for the other 4 weeks. This distinct design allowed for a conventional rigorous RCT of low risk of bias (Phase 1), and concomitantly resolved a potential inequity issue by providing access to iTBS for every participant (Phase 2) (Green, 2008). This also enabled investigating effects of longer treatment courses. Considering the feasibility based on their school activities, participants freely chose 2 intervention days, which are at least 48 hours apart from each other, from Monday to Saturday in the beginning of their interventions. Once they made the choice, the schedule of sessions was fixed throughout the trial.

Clinical assessments were completed in participants within one week of the first iTBS session of Phase 1 (Baseline) and Phase 2 (Week 5), following the last iTBS session (Week 8), as well as at follow-up (Week 12). With the same baseline and follow-up assessment schedule, social cognition was specifically measured within 1 hour following the last iTBS session of Phase 1 and 2, respectively.

A minimum total sample size of 68 was estimated using G\*Power 3.1 (Faul, Erdfelder, Buchner, & Lang, 2009), being powered (90% power and two-sided 5% significance) to detect a standardized effect at 0.4 from within-between interaction of the repeated-measure ANOVA model. The estimated effect size was guided using the pool effect on social behavior deficits in existing studies (Barahona-Correa et al., 2018).

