### Statistics

Herein we only reported clinical and cognitive data during RCT. Independent t-test and chi-square test were used to evaluate the difference of baseline characteristics. To simultaneously examine the immediate effect of pSTS vs. sham stimulation in different visits, the generalized estimating equations (GEE) model was conducted using the data of Baseline, Week 4, and Week 8. To account for correlations between individuals' repeated measurements between visits, a working correlation matrix with a first-order autocorrelation was used with the robust estimator of standard error. Treatment, Time, and a two-way interaction (Active vs. Sham  $\times$  Time) effects were modeled in the GEE. The maximum likelihood method in the GEE was used to address the missing values from dropouts. In consideration of high inter-individual variability in the clinical symptoms and social cognitive function at baseline, we also implemented an additional analysis using the symmetrized percentage change (Ayers, 2006) to investigate the iTBS effects. Because there was significant difference for both groups at baseline in the RMET, all of the analyses in the GEE and symmetrized percentage change were adjusted.

To comprehensively examine effects across time for both conditions, exploratory within-group comparisons were also conducted in the same GEE regardless of whether the main effect was statistically significant. However, when the main effect of GEE is not statistically significant, the significant findings in these exploratory within-group comparisons should be interpreted conservatively. The correction for multiple comparisons was implemented to avoid type-I errors. Five pairwise within-group comparisons (i.e., Baseline vs. Week 4, Baseline vs. Week 8, Baseline vs. Week 12,

Week 4 vs. Week 8, Week 8 vs. Week 12) were calculated separately in Active (8-week active TBS) and Sham (4-week sham followed by 4-week active TBS) groups.

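### Covariate adjustment was triggered by a significant baseline RMET test; it should be fixed in advance, with each score adjusted for its own baseline

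*Combined protocol and SAP*

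**What the plan says.** All of this is in the Statistics section unless noted.

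- Baseline comparison: "Independent t-test and chi-square test were used to evaluate the difference of baseline characteristics". No significance level is given for these tests.
- Trigger and consequence, in one sentence that closes by saying adjustment was made: "Because there was significant difference for both groups at baseline in the RMET, all of the analyses in the GEE and symmetrized percentage change were" […]. Neither the covariate nor the form of adjustment is stated.
- Model: a GEE with Baseline, Week 4 and Week 8 as outcome visits and terms for Treatment, Time and their interaction. An additional analysis uses the symmetrized percentage change, which also refers each score to its baseline.
- Outcomes (Outcomes section): the caregiver-rated SRS is the primary efficacy measure. With the RMET, the two Frith-Happe scores and the RBS-R, I count the five measurements for which the Statistics section sets a 0.01 threshold.
- Size (Design section): "A minimum total sample size of 68 was estimated using G\*Power 3.1". The allocation ratio is not given.

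**The concern.** A baseline significance test is a poor way to choose covariates. It answers whether the arms differ by more than chance, which randomisation has already settled. It ignores how strongly the variable predicts the outcome, which is what decides whether adjustment helps. The past tense also shows that the choice followed sight of the data.

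What is at stake is mainly the primary outcome. If the sentence covers the RMET analyses only, SRS gets no baseline covariate. If it covers every outcome, SRS is adjusted for a different measure. Either way SRS, the Frith-Happe scores and the RBS-R are not adjusted for their own starting values. The interaction term then behaves as a change-from-baseline contrast. That contrast removes the raw baseline difference but not regression to the mean: the arm that happens to start worse tends to show the larger apparent improvement.

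**Working it through.** **Inputs from the document.** Total 68; 90% power; two-sided 5%; standardized effect 0.4 for a within-between interaction; efficacy threshold 0.01.

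**Assumptions, because the document is silent.** 1:1 allocation, so 34 per arm; baseline tests at 5%; baseline to follow-up correlation ρ of 0.5 to 0.8; two visits in place of the three-visit GEE.

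**1. The plan's own figure.** For a repeated-measures interaction, λ = N·m·f²/(1 − ρ). With two groups, m = 2 visits, ρ = 0.5 and f = 0.2 (0.4 read as Cohen's d), λ = 68 × 2 × 0.04/0.5 = 10.88 on 1 and 66 df, and power is 0.9015. So 68 is reproduced. Reading 0.4 as f gives 20 instead (two visits, ρ = 0.5).

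**2. Largest observed imbalance that triggers nothing.** t(0.975, 66) × √(2/34) = 1.997 × 0.2425 = 0.484 SD. With 30 or 39 per arm it is 0.517 or 0.451 SD. With a 1% baseline test at 34 per arm it is 0.643 SD.

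**3. How often a sizeable imbalance falls below that limit.** The chance difference has SE 0.2425 SD. The probability that it lies between 0.35 and 0.45 SD in either direction is 2 × [Φ(1.856) − Φ(1.443)] = 2 × (0.9683 − 0.9255) = 8.6%. Simulation, counting only non-significant cases, gives about 8–9% per measure.

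**4. Bias left in the change contrast.** Expected shift = (1 − ρ) × imbalance, with sign opposite to the imbalance. At 0.40 SD this is 0.5 × 0.40 = 0.20 SD for ρ = 0.5 and 0.2 × 0.40 = 0.08 SD for ρ = 0.8. At the 0.48 SD limit it is 0.24 and 0.10 SD.

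**5. False positives.** Simulation of 60,000 null trials per ρ, 34 per arm. The second and third columns are restricted to trials with a non-significant imbalance above 0.35 SD (about 10% of trials). The rule simulated in the last column uses the change contrast when the score's own baseline test is non-significant, and ANCOVA otherwise.

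| ρ | Change contrast, restricted | Always ANCOVA, restricted | Test-then-adjust, all trials |
|---|---|---|---|
| 0.5 | 9.62% | 4.89% | 4.25% |
| 0.7 | 7.95% | 4.97% | 4.59% |
| 0.8 | 7.05% | 5.63% | 4.82% |

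In the narrower 0.35–0.45 SD band the change contrast rejects about 9% to 7% of the time at nominal 5%, and about 2% to 1.5% at nominal 1%.

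**6. Precision over all randomisations.** SD of the estimate, test-then-adjust against always ANCOVA: 0.234/0.211 = 1.11 at ρ = 0.5 and 0.152/0.147 = 1.03 at ρ = 0.8. Compared with never adjusting, ANCOVA has (1 + ρ)/2 of the variance: 0.75 to 0.90.

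**7. What the trigger tells us.** With five independent tests at 5%, at least one is significant by chance in 1 − 0.95⁵ = 22.6% of trials. A significant RMET difference is therefore unremarkable and carries no message about which scores need adjustment.

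**The case against.** The strongest reply is that baseline is already in the model. Each score's baseline is an outcome visit and the interaction contrasts changes, so the raw imbalance does not pass into the between-arm result. That stands. Only the (1 − ρ) remainder and the lost precision are at issue. Averaged over randomisations, false positives do not exceed the nominal level, and at the plan's 0.01 threshold the conditional excess is small in absolute terms.

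Three stronger readings are tempting, and the document supports none of them.

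- A reader might cite the low power of a t-test at 34 per arm and say that it often misses a half-SD imbalance. That power refers to a true difference between populations, which randomisation excludes. An observed 0.5 SD difference gives t = 0.5/0.2425 = 2.06, p = 0.043, and would be flagged.
- A reader might say that the plan takes a non-significant test as proof that the arms are balanced. The text says only that differences were evaluated and that a significant one led to adjustment.
- A reader might say that the five scores are analysed by different models. If the sentence covers every outcome, they share one adjustment.

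A generous reader could also suppose that adjusted means each score's own baseline. The text does not say so, and its only stated reason concerns RMET. If that was done, naming the covariate would remove the bias described here, though not the fact that a baseline test prompted it.

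**Conclusion.** The point holds in a limited form. The decision to adjust rests on an observed baseline test, the covariate and scope are unstated, and on either reading of the sentence the primary SRS lacks adjustment for its own baseline. The harm is conditional bias in an unlucky minority of randomisations and a modest loss of precision; there is no general inflation of type I error. If the planned 0.4 is a Cohen's d, as the reproduced sample size suggests, a bias of 0.20 SD would be half of it, but only at the low end of ρ.

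All sizes depend on assumed values: equal arms of 34, a 5% baseline test, ρ of 0.5 to 0.8 and the two-visit simplification. The criticism of the selection rule does not depend on them.

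**What to change.** Replace the sentence with a rule that does not look at baseline p-values, for example: *Each of the five scores is analysed with adjustment for its own baseline value, whatever any baseline comparison shows.*

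- In the GEE, either take the post-baseline visits as outcomes with the baseline score as covariate, or keep baseline as an outcome visit and constrain the arms to a common baseline mean. A baseline covariate cannot simply be added to a model in which baseline is itself an outcome.
- Apply the same rule to the symmetrized percentage change analysis.
- Keep the baseline table as description (means, SDs, standardized differences) and state that the t and chi-square tests decide nothing in the analysis.
- Name the covariate and scope of the adjustment already made, label it as data-driven, and show the RMET result with and without it.

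The cost is one degree of freedom per model, a change in model layout and a refit, and estimates may move slightly. The baseline data are already collected, so no new participants or visits are needed.

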## Outcomes

The primary outcomes included the safety profiles, as well as the social deficits as measured by the caregiver-rated Social Responsiveness Scale (SRS) (Gau, 2013), since theoretically targeting the pSTS is aimed to modulate the activity within the social brain network. Atypical social cognition is often associated with the autistic symptoms. The secondary outcomes thus included two common tasks assessing the social cognition performances of people with ASD (Barahona-Correa et al., 2018), i.e., the Reading the Mind in the Eyes test (RMET) (Baron-Cohen, Wheelwright, Hill, Raste, & Plumb, 2001; T. S. Li et al., 2020) and Frith-Happe Animations Task (White, Coniston, Rogers, & Frith, 2011) (Barch et al., 2013). Notably, these two tasks, nonetheless, are not specific to the pSTS activities. Given our preliminary beneficial results in compulsory behaviors in adults (Ni et al., 2017), we also adopted the Repetitive Behavior Scale-Revised (RBS-R) (Bodfish, Symons, Parker, & Lewis, 2000; Y. C. Yang et al., 2019) as the exploratory outcome. Higher scores on the SRS and RBS-R represent greater severity of the two domains of autistic symptoms. RMET total scores represent how many correct mental states the participant has inferred from the eyes, indicating

individual's theory of mind capability. Frith-Happe Animations also tap mentalizing capacity by asking the participant to infer whether interaction intents exist between two triangles. When the participant answered about the presence/absence of interactions, he/she was further asked to select words that best described how these triangles were feeling at the end of each video clip. Participants scored 1 point for correct answers to either presence/absence or exact description of mental states, which are summarized as the total Categorical scores and Feelings scores, respectively. To enhance a contrast and reduce assessment time, we adopted the revised Frith-Happe Animations following those used in the Human Connectome Project (Barch et al., 2013), which only included social and random interactions.

Side effects were assessed immediately after each session and at one-month follow-up using open-ended questions inquiring any physical discomfort and then close-ended questions including "pain at application site", "headache/dizziness", "tinnitus" and "anxiety" experienced during and after iTBS

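### The plan does not say how the analyses were adjusted for the RMET baseline difference, and a baseline main effect would leave the GEE Treatment × Time contrast unchanged

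*Combined protocol and SAP*

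**What the plan says.** All of this is in the Statistics section of the combined protocol and SAP unless noted.

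- Outcome rows: "the generalized estimating equations (GEE) model was conducted using the data of Baseline, Week 4, and Week 8". Baseline is therefore a response, not only a covariate.
- Model terms: "Treatment, Time, and a two-way interaction" of arm with time. No covariate of any kind appears in this list.
- Correlation and standard errors: "a working correlation matrix with a first-order autocorrelation was used with the robust estimator of standard error".
- Adjustment: the reason given is a "significant difference for both groups at baseline in the RMET, all of the analyses in the GEE and symmetrized percentage change were adjusted". The sentence stops there, and no other section describes the adjustment.
- Missing data: "The maximum likelihood method in the GEE was used to address the missing values from dropouts".
- Within-arm changes: "exploratory within-group comparisons were also conducted in the same GEE regardless of whether the main effect was statistically significant".
- Role of RMET (Outcomes section): "The secondary outcomes thus included two common tasks assessing the social cognition performances of people with ASD"; RMET is one of the two. The caregiver-rated SRS is a primary outcome.
- Size (Design section): "A minimum total sample size of 68 was estimated", for 90% power at two-sided 5% and a standardized effect of 0.4. The end of the Statistics section sets significance for the GEE at 0.01.

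**The concern.** A reader will take the adjustment sentence to mean that the RMET group comparison has been corrected for a known imbalance. Whether it has depends on the detail that is left out. With Baseline among the outcome rows and a full Treatment × Time structure, one common way of adjusting (adding baseline RMET as a covariate) does nothing to the contrast of interest. The same covariate would have a real effect in the symmetrized percentage change analysis, where Baseline is not an outcome row. The two RMET analyses could then disagree for that reason alone, and nothing in the plan would let a reader see it.

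The phrase about all analyses is also open. It could mean that only the RMET models were adjusted, or that every measure was adjusted for baseline RMET. In the second case a main effect cancels from those GEEs too. For no measure does the plan name that measure's own baseline as a covariate, although every patient's baseline is collected.

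**Working it through.** **1. The plan's own figure.** The sample size of 68 is reproduced by the noncentral F calculation for a within-between interaction, with 0.4 read as a standardized difference (f = 0.4/2 = 0.2), two groups, m = 2 visits and rho = 0.5. The visit count and rho are inferred from the match. Noncentrality = f² × N × m/(1 − rho) = 0.04 × 68 × 2/0.5 = 10.88, and power is 0.9015. With 34 per arm and change variance 2(1 − 0.5) = 1, noncentrality is also 17 × (difference in change)². The difference in change is therefore √(10.88/17) = 0.8 SD.

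**2. Cancellation.** Write the mean at visit t in arm g as a_t + b_t·g + c·x, with x the patient's baseline value. The term c·x is the same at all three visits of a patient. With complete data the interaction estimate is therefore (change in Active) − (change in Sham), whatever c is.

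Check on one simulated null data set (68 patients, baseline gap −0.484 SD, rho 0.5, AR(1), robust SE):

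| Model | Week 4 Treatment × Time (SE) |
|---|---|
| No covariate | 0.38778 (0.21169) |
| Baseline main effect | 0.38778 (0.21169) |
| Baseline × Time | 0.14203 (0.18463) |

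The first two equal the raw difference in mean change. The third equals a Week 4 ANCOVA on baseline.

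With dropout (assumed 9% by Week 4 and 17% by Week 8, gap of 0.484 SD, rho 0.5, 1,200 data sets) the mean Week 4 bias was −0.234 SD with no covariate, −0.232 with a main effect and 0.009 with baseline × Time. In single data sets the main effect moved the estimate by 0.007 to 0.020 SD on average across the values of rho tried, and by 0.124 SD at most.

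**3. What is left in the RMET contrast.** A difference in change subtracts the observed gap in full. Given a gap D, the expected later gap with no treatment effect is rho × D, so the contrast is off by −(1 − rho) × D: the arm that started higher appears to gain less. The plan does not give D. At 34 per arm and a 0.05 test, the smallest significant gap is t(0.975, 66) × √(2/34) = 1.997 × 0.2425 = 0.484 SD.

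| rho, baseline to Week 4 (assumed) | (1 − rho) × 0.484 |
|---|---|
| 0.3 | 0.34 SD |
| 0.5 | 0.24 SD |
| 0.7 | 0.15 SD |
| 0.8 | 0.10 SD |
| 0.9 | 0.05 SD |

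At exactly this gap the change-test statistic is approximately normal with mean 1.997 × √((1 − rho)/2) and variance (1 + rho)/2. Null rejection at the plan's 0.01 level is then 3.4% at rho 0.5 and 2.1% at rho 0.8.

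**4. Precision for every measure.** Variance of a change score is 2(1 − rho)σ²; adjusted for own baseline it is (1 − rho²)σ². The ratio is (1 + rho)/2, so adjustment saves 25%, 15%, 10% and 5% of the variance at rho 0.5, 0.7, 0.8 and 0.9. Under the reading that reproduces 68 (0.8 SD, rho 0.5, 34 per arm), the noncentral t parameter rises from 0.8 × √17 = 3.30 to 3.30/√0.75 = 3.81. Power at 0.01 goes from 74% to 87%.

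**The case against.** The strongest reply has four parts.

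First, a reader might infer that a main effect was probably used, because no covariate × Time term is listed. The documents do not support that. The list of terms omits any covariate main effect as well, so it is silent on the form. This stands, and the cancellation must be put conditionally.

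Second, a reader might infer that the baseline gap itself remains in the RMET result. It does not: the interaction is a difference in change. Only regression to the mean remains.

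Third, over all randomizations the change contrast is unbiased and keeps its size: 200,000 simulated null trials gave 1.0% rejection at the 0.01 level at both rho 0.5 and rho 0.8. This is right. The shift in step 3 arises only once one conditions on the observed imbalance. Conditioning is reasonable here because the plan itself reports a significant imbalance and claims to have dealt with it.

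Fourth, RMET is one secondary task, and unadjusted contrasts for the other measures are valid, so asking for own-baseline adjustment everywhere could be called preference. The validity is granted. But the precision gain uses data already in hand and is not trivial at moderate correlation, so it remains a worthwhile improvement rather than the repair of an error.

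**Conclusion.** The firm defect is that the covariate, its form and the models it enters are not stated. The consequence is conditional: if baseline entered the GEE as a main effect only, the RMET Treatment × Time contrast was in effect not adjusted. The residual shift at Week 4 would then be about 0.24 SD at rho 0.5 and 0.10 SD at rho 0.8 for the smallest significant gap. A larger gap gives a proportionally larger shift. These sizes assume 34 per arm (68 is only a minimum), a baseline test at 0.05, and values of rho that the plan does not give. The direction is unknown because the plan does not say which arm started higher.

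A reader might go further and conclude that the primary SRS result is biased. Nothing in the documents supports that: the only baseline difference that this section reports as significant is in RMET. For SRS, RBS-R and the two animation scores the cost of leaving out the measure's own baseline is precision alone.

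A separate and minor wording error is the reference to maximum likelihood within GEE. Ordinary GEE solves estimating equations and has no likelihood to maximize. This adds nothing to the weight of the main point.

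**What to change.** State which covariate was used, in what form, and in which models. Then, for each measure, estimate the Week 4 and Week 8 group differences with that measure's own baseline in a form that affects the contrast:

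- add baseline × Time (with the baseline main effect) to the existing GEE; or
- use only the post-baseline visits as outcomes, with baseline and baseline × visit as covariates.

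In a complete simulated data set the two gave the same estimate and robust SE, 0.35154 (0.19898), so the GEE can be kept. The document is written in the past tense; if the data have already been analysed, report this as a re-analysis. If baseline × Time was in fact used for RMET, one sentence saying so settles the RMET question.

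Replace the maximum-likelihood sentence with a statement that GEE uses all available visits and generally needs a stronger missing-data assumption than a likelihood model.

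The cost is a small re-analysis of data already collected, plus wording. In the post-baseline form, patients with no post-baseline value contribute nothing, and the exploratory within-group comparisons with Baseline must be run separately. In the baseline × Time form those comparisons refer to a stated baseline value, such as the overall mean, and will differ somewhat from raw within-arm changes.

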Considering clinical heterogeneity in ASD, we defined responders based on the Reliable Change Index (RCI) calculated using the SRS total scores. The RCI takes into consideration the false positive outcome that could occur due to random error from repeated measurements alone (Jacobson & Truax, 1991). The RCI represents differences in individual's scores between before- and after-intervention, divided by the standard error of the difference of the measure. Responders were those with RCI  $>1.64$ , which corresponds to  $p<0.05$  with one-sided test (i.e., the null hypothesis was that iTBS would not help with social symptoms). Demographic and clinical features were compared between the responders and non-responders using non-parametric tests.

In addition to the stratified analysis based on responsiveness, we also tested a three-way interaction (Active vs. Sham  $\times$  Time  $\times$  Modifier) to explore whether iTBS over the pSTS is more beneficial for individuals with ASD with certain characteristics. Effect modifiers included demographics, intelligence quotient, clinical traits, comorbidity, and medication.

Statistical analysis was performed using the SAS Version 9.4 software (SAS Institute, Cary, NC, USA). Considering multiple comparisons including the clinical symptoms and social cognitive function (5 measurements), the GEE, within-group analyses and three-way interaction were considered statistically significant at  $p\text{-value}\leq0.01$ . Despite contention, herein, alpha level in-between 0.01 and 0.05 were considered a nominal significance for hypothesis generating for the future study (Bays, 2019).

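### The responder comparison of features cuts the continuous SRS change at RCI >1.64, which under plausible but undocumented inputs costs roughly 10 to 29 points of power in a secondary analysis

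*Combined protocol and SAP*

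**What the plan says.** In the Statistics section, "we defined responders based on the Reliable Change Index (RCI) calculated using the SRS total scores". The index is each child's before-to-after difference, "divided by the standard error of the difference of the measure", and a responder is a child whose index exceeds 1.64. That threshold is a one-sided 5% criterion applied child by child. The only use then described for the split is this: "Demographic and clinical features were compared between the responders and non-responders using non-parametric tests".

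The next paragraph adds a second search: "we also tested a three-way interaction (Active vs. Sham" by time by modifier, "to explore whether iTBS over the pSTS is more beneficial for individuals with ASD with certain characteristics". It involves no responder cut. "Effect modifiers included demographics, intelligence quotient, clinical traits, comorbidity, and medication".

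On thresholds, "the GEE, within-group analyses and three-way interaction were considered statistically significant at" 0.01, and results between 0.01 and 0.05 count as nominal. The responder comparison is not on that list and has no stated alpha. The section also does not say which visits or arms enter it, what share of responders is expected, or how strong an association it should detect.

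**The concern.** The divisor of the RCI is a property of the measure and so is the same for every child. RCI >1.64 is therefore a fixed cut on the SRS change. A child at 1.6 is grouped with a child at 0, and a child at 1.7 with a child at 5.

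The stated reasons are clinical heterogeneity and protection against false positives from measurement error. The second is a good reason not to mislabel one child. It does not help the group comparison, because a rank test on the uncut change already holds its type I error.

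At stake is the reading of a non-significant result. With about 68 children, a real association between a feature and SRS change may be reported as no difference between responders and non-responders, partly because the outcome was cut.

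**Working it through.** **Inputs from the documents.** The minimum total is 68 (Design). The cut is RCI >1.64, and the feature tests are non-parametric (Statistics). An arm of 34 assumes 1:1 allocation, which is not stated.

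**The plan's own figure.** The plan has no power figure for the responder comparison. Its 68 does reproduce for the main test if the standardized effect of 0.4 is read as d, so f = 0.2, with two time points and a correlation of 0.5 (both assumed): λ = N·f²·m/(1−ρ) = 68 × 0.04 × 2 / 0.5 = 10.88, giving power 0.902. So 68 is used below as the sample size.

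**Assumed inputs.** Feature and SRS change are bivariate normal with correlation r. The responder share is p. The test is two-sided at 5%.

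**Information kept by the cut.** Asymptotic efficiency relative to the uncut normal score is φ(z_p)² / [p(1−p)]:
- p = 0.50: 0.3989² / 0.25 = 0.64, so 36% is lost
- p = 0.35: 0.3704² / 0.2275 = 0.60, so 40% is lost
- p = 0.20: 0.2800² / 0.16 = 0.49, so 51% is lost

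Even the most favourable split makes 68 children count as about 68 × 0.64 ≈ 43. At 20% responders it is about 68 × 0.49 ≈ 33.

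**Power by simulation** (4000 to 6000 replicates per cell). Uncut is Spearman of feature with SRS change. Cut is Mann-Whitney of the feature by responder status.

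| N | r | Uncut | Cut, 20% responders | Cut, 50% responders | Loss in points |
|---|---|---|---|---|---|
| 68 | 0.3 | 66% | 38% | 49% | 28 to 17 |
| 68 | 0.4 | 90% | 63% | 75% | 27 to 15 |
| 34 | 0.3 | 37% | 21% | 26% | 16 to 11 |
| 34 | 0.4 | 61% | 33% | 43% | 28 to 18 |

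Repeat runs moved single cells by up to about 3 points. Over all runs the loss for r 0.3 to 0.4 and 20 to 50% responders was 14 to 29 points at N = 68 and 10 to 29 at N = 34. The lower end for one arm was between 10 and 13, depending on the run.

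**Binary feature.** With 50% prevalence, a 0.8 SD difference in change and N = 68, Mann-Whitney on the uncut change has 88% power. Chi-square on responder status has 62 to 72%, a loss of 16 to 26 points.

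**Outside the central range:**
- Smaller: about 5 to 9 points at r = 0.2 in one arm of 34, and about 6 to 8 at r = 0.5 with N = 68 and 35 to 50% responders, where power is near its ceiling.
- Larger: about 10 to 49 points if only 10% respond, over r 0.2 to 0.5 and both sample sizes.

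**Type I error.** At r = 0 both tests reject about 4 to 6% of the time, so the cut buys no error control.

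**The three-way interaction.** With a slope in the Active arm only and 34 per arm, its simulated power at r = 0.3, 0.4 and 0.5 is about 8%, 17% and 32% at 0.01. At 0.05 it is about 25%, 37% and 55%. Only the 0.05 figures may fairly be set beside the table above.

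**The case against.** **The plan already looks for features without a cut.** This is true, and a reader might infer from the responder paragraph alone that it does not. The three-way interaction uses the full scale and covers demographics, IQ, clinical traits, comorbidity and medication, and it is the analysis to which the plan gives the question of who benefits more from iTBS. But it tests whether the Active-Sham difference varies with a feature. The responder comparison asks which features go with change. The plan presents the two side by side, so the first does not repair the second.

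**The analysis is secondary.** This also stands. A reader might infer that cutting the SRS weakens the efficacy result. It does not: the SRS is analysed by GEE on the scores, with symmetrized percentage change as a supplement, and neither is cut.

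**The size is not fixed by the documents.** Correlation, responder share, arms, visits and alpha are all unstated. No single unconditional figure is supported, only a range tied to its assumptions.

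**Associations will not necessarily be missed.** With 68 children and r = 0.4, the cut test still has 63 to 75% power, so the figures support only that associations may be missed.

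**Uncut change has limits too.** Without an arm contrast, an association with change mixes prognosis and regression to the mean with response to iTBS. This applies equally to the responder split, and it limits what either analysis can claim.

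**Swapping analyses now would be post hoc.** The plan is written in the past tense and already reports a baseline RMET difference. This is a reason to keep the RCI split visible and to label the uncut analysis exploratory.

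**Conclusion.** The point holds in a limited form. The responder comparison discards information from a continuous SRS change and gains no error control for the group test. For r 0.3 to 0.4, 20 to 50% responders, two-sided 5% and normally distributed change, the loss is about 14 to 29 points with 68 children and about 10 to 29 in one arm of 34. It can be as small as about 5 points, or approach 49 if few children respond. The direction is the same in every non-null setting examined; only the size depends on inputs that the documents do not give.

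The consequence is confined to a secondary, descriptive analysis, where a null finding would be weaker evidence than it appears. This is an inexpensive improvement, not a defect in the trial's main result.

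**What to change.** In the Statistics section:
- Keep the RCI >1.64 rate and the responder versus non-responder table as description only.
- Base inference about features linked to SRS change on the uncut SRS total change, over the same visits and participants. Use Spearman correlation for continuous features and Mann-Whitney or Kruskal-Wallis on the change score for categorical ones. This keeps the plan's non-parametric approach.
- A regression of post-treatment SRS on the feature with baseline SRS as covariate is an alternative, not an equivalent. The two can differ when the feature correlates with baseline SRS, and the regression cannot test baseline SRS itself as a feature.
- State which visits and arms are used and what threshold applies, since none of these is given now.
- Label the analysis exploratory, and describe results as associations with change. Leave modification of the Active-Sham difference to the three-way interaction.

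The cost is a few sentences of text and a few lines of code on data already collected. The downside is that an association with points of change is slightly harder to communicate than a responder profile; the retained descriptive table covers that.
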